If the AE resolves, subjects will be restarted on a lower dose of over encapsulated rosuvastatin. Subjects on rosuvastatin 20 mg or 40 mg will be restarted on rosuvastatin 10 mg, and subjects on 5 mg or 10 mg will be restarted on rosuvastatin 5 mg. Subjects taking over-encapsulated placebo will be restarted on placebo. In the event that the AE re-occurs upon re-initiation at the lower dose, over encapsulated rosuvastatin/placebo should be discontinued. If the AE does not re-occur with the lower dose, an increase in the over encapsulated rosuvastatin dose may be considered at the subsequent clinic visits according to the protocol algorithm. If the AE re-occurs following administration of this new dose of

rosuvastatin, over encapsulated rosuvastatin/placebo may be reverted to the last tolerated dose. Aldafermin dosing will not be interrupted.

If a subject experiences a statin-related AE of myalgia or rhabdomyolysis (as determined by the PI), information will be collected on the AE including the specific description, history, and severity based on CTCAE grading and forwarded to the designated third-party Medical Monitor who is blinded to treatment assignment but unblinded to laboratory data and statin assignment and dose. The clinical study team will collect a blood sample for safety laboratory evaluations within 48-72 hours. For subjects that have signs or symptoms suggestive of rhabdomyolysis from either muscle symptoms (such as myalgia, pain, weakness, dark urine) or elevated creatine kinase (CK), the origin of the symptoms/CK elevation will be investigated. To this end, the subject will be interviewed about recent heavy exercise, trauma, convulsions, surgery, use of excessive alcohol, morphine, cocaine, or other contributing factors. Additional laboratory tests (creatinine, AST/ALT, total and conjugated bilirubin, potassium, calcium, and/or myoglobin (serum and urine)) will also be performed.

If the subject experienced statin-related increased CK>3 x ULN with clinical symptoms, administration of over-encapsulated rosuvastatin/placebo should be held and may be re-initiated at half the prior dose if follow-up CK is <3 x ULN. If CK rises to >3 x ULN again, the administration of over-encapsulated rosuvastatin/placebo should be held until CK <3 x ULN and can be re-initiated at 5 mg. For subjects experiencing symptoms and CK elevation on 5 mg, over-encapsulated rosuvastatin/placebo should be discontinued.

Aldafermin dosing will continue.

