For subjects with suspicion of statin-related myalgia or rhabdomyolysis AND CK 3-5 x ULN, administration of over-encapsulated rosuvastatin/placebo should be held until CK<3 x ULN and may be reinitiated at half the original dose. If symptoms persist and if CK increases >3 x ULN, rosuvastatin should be discontinued. For CK>5 x ULN with clinical suspicion of rhabdomyolysis (ruling out other causes, e.g., recent heavy exercise, trauma, convulsions, surgery, use of excessive alcohol, morphine, cocaine, or other contributing factors), rosuvastatin will be discontinued. Throughout, aldafermin dosing should continue.

iii) Laboratory value(s) suggestive of DILI:

- a) Elevation of AST or ALT >2 x above subject-specific baseline value (calculated using the average of the Day -56 and the Day 1 values) and total bilirubin >1.5 x subject specific baseline value, repeat testing of ALT, AST, and bilirubin must be performed within 48-72 hours. If there are persistent elevations (AST or ALT >2 x baseline or TBL >1.5 x baseline values) upon repeat testing, then close observation (testing and physical examination 2-3 times per week) should be implemented and discontinuation of aldafermin and rosuvastatin should be considered (see below). Note: the unblinded study Medical Monitor will be notified of acute suspected cases and upon identification of suspected DILI cases, the Liver Events Adjudication Committee chair will be notified.
- b) A decision to discontinue or temporarily interrupt the study drug will be considered based on factors that include how much higher than baseline ALT and AST were relative to the ULN and how much the on-study ALT and AST levels have increased

relative to baseline, in addition to whether there is concomitant elevation of bilirubin or INR. aldafermin and rosuvastatin will be discontinued or temporarily interrupted as follows:

- If baseline measurements (BLM) were $<2 \times$ ULN, discontinue if ALT or AST increases to $>5 \times$ BLM
- If BLM $\geq 2 \times$ ULN but $<5 \times$ ULN, discontinue if ALT or AST increases to $>3 \times$ BLM
- Discontinue if ALT or AST increase $>2 \times$ BLM AND the increase is accompanied by a concomitant increase in TBL to $>2 \times$ BLM OR the INR concomitantly increases by >0.2
- Discontinue if total bilirubin $>3.0 \text{ mg/dL}$
- In any subjects with signs and symptoms of fatigue, nausea, vomiting, right upper quadrant pain or tenderness, fever, rash, and/or eosinophilia ($>5\%$).

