c) If a subject resides in a remote area, laboratory testing can be performed locally, and the results should be promptly communicated to the investigator site.

d) Close observation for suspected DILI will include:

- Repeating liver enzyme and serum bilirubin tests two or three times weekly. Frequency of repeat testing can decrease to once a week or less if abnormalities stabilize or the study drug has been discontinued and the subject is asymptomatic.
- Obtaining or re-confirming a detailed history of symptoms and prior or concurrent diseases.
- Obtaining or re-confirming the history of concomitant drug use (including nonprescription medications and herbal and dietary supplement preparations), alcohol use, recreational drug use, and special diets.
- Ruling out acute viral hepatitis types A, B, C, D, and E; autoimmune or alcoholic hepatitis; NASH hypoxic/ischemic hepatopathy; and biliary tract disease.
- Obtaining a history of exposure to environmental chemical agents.

Outside of situations listed above, no aldafermin/matched placebo dose reductions will be allowed. Temporary drug holidays from aldafermin dosing <5 days will be allowed on a case-by-case basis for subjects for safety or tolerability but must be approved by the sponsor Medical Monitor or designee. If drug is restarted and is still not tolerated, the subject should stop the medication as multiple drug holidays will not be allowed.

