8. STUDY PROCEDURES

8.1. Schedule of Study Procedures

The Schedule of Study Procedures is shown in [Table 8](#). The visits should occur as close to the intended dates as possible. However, there is an acceptable ± 3 -day window from Week 2 through Week 6, and Week 54 (Week 58 if needed). Visit window from Weeks 12 through 48 is ± 7 days. Visit window for Week 49 is $+3$ days.

Subjects attending any visits out of windows from Day 1 to Week 48/Early Withdrawal (EOT) visit should be brought back into compliance with the overall study visit schedule as soon as possible thereafter.

The PI has discretion to repeat assessments if he/she believes the results are erroneous or to rule out worsening of liver disease (Exclusion #7) for Day -56 and Day -42 visits. Repeat assessments must be conducted within the 8-week Screening Period. The screening window may be increased up to 16 weeks (112 days) to obtain all screening assessments, with Medical Monitor approval. Only assessments that need to be repeated should be done rather than a full re-screening of the subject. The results of the repeat testing will be used for evaluation.

All subjects will be assessed at Weeks 49 and 54 to confirm their LDL-C levels have returned to near baseline. At that point, no additional follow-up will be performed.

Subjects who do not meet criteria at Week 54 (Day 1 levels within 15 mg/dL or at the protocol-defined LDL-C goal) will have an additional 4-week follow-up visit at Week 58 to confirm that their LDL-C level returned to near baseline or at the protocol-defined LDL-C goal. Subjects may remain on over-encapsulated rosuvastatin through Week 58.

All subjects will have pre-dose PK blood collection on all treatment visits as well as 4-hours post-dose on Day 1, Week 24, and Week 48.

All subjects will be offered the opportunity to participate in a PK sub-study, which will involve a few additional procedures, including blood draws (i.e., on Day 1 and Week 48 at pre-dose, and post-dose at 0.5, 1, 2, 4, 6, 8, 12, and 24 hours). Reference [Table 8](#) for more details.

Table 8. Schedule of Assessments

| Study Procedure | Screening [a] | | Treatment Visits | | | | | | | | | | Follow-up | | LDL-C monitor |
|--|------------------|---------------|------------------|------|------|-------|-------|-------|-------|-------|-------|----------------------|-----------|----------------|------------------|

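### The mandatory 48-72 h liver repeat needs an enzyme rise AND a bilirubin rise, so an asymptomatic isolated rise below the stop limits gets an early repeat only if someone judges it necessary

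*Protocol*

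**What the plan says.** Protocol 7.1.1 iii) sets out the actions for laboratory values suggestive of drug-induced liver injury (DILI).

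- **Part a), first repeat.** AST or ALT above twice the subject's baseline (the average of Day -56 and Day 1) "and total bilirubin >1.5 x subject specific baseline value, repeat testing of ALT, AST, and bilirubin must be performed within 48-72 hours".
- **Part a), persistence.** "If there are persistent elevations (AST or ALT >2 x baseline or TBL >1.5 x baseline values) upon repeat testing", close observation starts and stopping both drugs is considered.
- **Part b), stop bullets.** Bullets 1 and 2 act on ALT or AST alone. Bullet 1, opening "If baseline measurements (BLM) were" below 2 x ULN, stops above 5 x baseline. Bullet 2 covers baselines from 2 to below 5 x ULN and stops above 3 x. Bullet 3 stops above 2 x "AND the increase is accompanied by a concomitant increase in TBL to" more than 2 x baseline, or with an INR rise above 0.2. Bullet 4 begins "Discontinue if total bilirubin" and sets 3.0 mg/dL. Bullet 5 lists symptoms and eosinophilia, with no enzyme threshold.
- **Part d).** "Close observation for suspected DILI will include" liver tests two or three times weekly.

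Table 8, footnote j, blinds ALT, AST and lipids to site and sponsor from Week 2. Bilirubin is not on that list. Section 7.1.1 ii) describes the third-party Medical Monitor as someone "who is blinded to treatment assignment but unblinded to laboratory data and statin assignment and dose". Sections 4.1 and 8.3.17 also give that monitor the related safety data.

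**The concern.** The same two limits are joined by AND for the first repeat and by OR for persistence. An isolated rise is therefore serious enough to justify close observation at a second test, but not to require that second test. Three of the stop bullets act on a single marker, yet no mandated repeat lies on the way up to any of them.

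The subjects have compensated cirrhosis. ALT and AST are also hidden from the treating site, so the investigator cannot respond to an isolated enzyme rise unless told of it. An explicit numeric trigger matters more in that setting. What is at stake is how soon a moderate isolated rise is confirmed.

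**Working it through.** No sample size or power figure is involved. The check applies the written rules to isolated rises.

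**Notation.** a = ALT or AST as a multiple of its baseline; t = total bilirubin (TBL) as a multiple of baseline; b = ALT/AST baseline in x ULN; t0 = TBL baseline in mg/dL; d = INR rise.

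**Rules (7.1.1 iii).**
- Mandatory repeat: a > 2 AND t > 1.5.
- Stop: (b < 2 and a > 5), or (2 <= b < 5 and a > 3), or (a > 2 and [t > 2 or d > 0.2]), or t x t0 > 3.0 mg/dL, or the symptom item.

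**Isolated enzyme rise** (t <= 1.5, d <= 0.2, no symptoms). The repeat cannot fire, and only bullets 1 and 2 can stop. The uncovered band is 2 < a <= 5 if b < 2, and 2 < a <= 3 if 2 <= b < 5.

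| Baseline (x ULN) | Band starts above | Band ends at |
|---|---|---|
| 1.0 | 2 x 1.0 = 2.0 x ULN | 5 x 1.0 = 5.0 x ULN |
| 1.9 | 2 x 1.9 = 3.8 x ULN | 5 x 1.9 = 9.5 x ULN |
| 3.0 | 2 x 3.0 = 6.0 x ULN | 3 x 3.0 = 9.0 x ULN |

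**Isolated bilirubin rise** (a <= 2, no symptoms). The repeat cannot fire, and only bullet 4 can stop. The band runs from above 1.5 x t0 to 3.0 mg/dL. The baselines below are the Inclusion 10a limit of 1.3 mg/dL, that limit with its 10% allowance (1.3 x 1.10 = 1.43), and an assumed low value of 0.5.

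| Baseline (mg/dL) | Band starts above | Band ends at |
|---|---|---|
| 0.5 (assumed) | 1.5 x 0.5 = 0.75 | 3.0 (6.0 x) |
| 1.3 | 1.5 x 1.3 = 1.95 | 3.0 (3.0/1.3 = 2.3 x) |
| 1.43 | 1.5 x 1.43 = 2.15 | 3.0 (3.0/1.43 = 2.1 x) |

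**Other repeat rules.**
- 7.1.1 ii): repeats follow a suspected statin-related AE.
- 7.1.1 iii) d): testing two or three times weekly presupposes that DILI is already suspected.
- 8.1: "The PI has discretion to repeat assessments if he/she believes the results are erroneous", or to rule out worsening at the two screening visits.
- 7.1.1 i): the Grade 3/4 rule governs stopping or interruption, not repeat testing.

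None of these orders a repeat because of an isolated rise as such.

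**Time to the next scheduled chemistry.** From the Week 6 visit through the Week 42 visit, the next visit is 6 x 7 = 42 days away. With windows at opposite extremes the maximum is 42 + 3 + 7 = 52 days for Week 6 to 12, and 42 + 7 + 7 = 56 days from Week 12.

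**Check of the OR wording.** At a = 2.1 and t = 1.0 the current rule does not fire; with OR it does.

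**The case against.** The strongest reply is that isolated rises are supervised even though no rule forces a repeat. This largely stands, and it limits the point.

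- **A reader might infer that isolated rises go unseen.** The protocol does not support that. The third-party monitor receives laboratory data and may act. Bilirubin is visible to the site, the sponsor and the monitors, so it is not left to the site alone. DILI can be suspected without meeting the part a) numbers, and the DSMB and liver adjudication committee oversee the trial. All of these routes depend on judgement, though. The monitor's described task is rosuvastatin titration, and no section assigns that monitor a duty to order a liver repeat for an isolated rise.
- **A reader might also infer that the mandated repeat exists only just below a stop rule.** Counting only repeats that come before bullet 3, the zone is indeed narrow: ALT/AST above 2 x with TBL above 1.5 and up to 2 x, or 1.95 to 2.6 mg/dL at a baseline of 1.3. But the combined trigger has no upper limit. It also applies above every stop threshold, where a repeat is still useful, for instance after a temporary interruption.
- **The asymptomatic group may be modest.** Bullet 5 lists fatigue, nausea and vomiting, and 2.8 reports gastrointestinal symptoms and fatigue as common on this drug. The protocol does not allow the remaining group to be sized.
- **Low prior risk.** Section 2.7 reports falling ALT and AST on aldafermin, and 2.8 expects no added liver-injury risk. That lowers the expected frequency but does not justify the mismatch of connectors.
- **A bare OR would over-trigger.** With a baseline of 0.5 mg/dL it would force a visit above 0.75 mg/dL, well inside the 1.3 mg/dL entry limit. This objection is right, and the fix needs a floor.

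**Conclusion.** The point holds as a gap in a mandatory safety step, and it is worth an amendment. An asymptomatic isolated rise without an INR rise above 0.2 has no rule-mandated early repeat in the three bands derived above. The practical consequence is a possible wait until the next scheduled visit, nominally 42 days from Week 6 onward, if nobody exercises judgement sooner. The 52- and 56-day figures are outer limits.

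The point does not show that liver safety is unmonitored or that large rises go unchecked, since the stop bullets, symptom item and monitor review remain in force. Nor do the documents settle whether AND was chosen deliberately or is a drafting slip; the adjacent OR makes a slip plausible.

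Assumptions: the limit in part a) means more than 2 x baseline, as the persistence sentence restates it; the laboratory data seen by the third-party monitor include ALT and AST; and no charter or laboratory manual, none of which is shown, adds a repeat rule.

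A secondary and rare gap: bullet 2 ends below 5 x ULN, while Inclusion 10e and 10f admit exactly 5 x ULN. Such a subject has no enzyme-only stop limit, although bullets 3 to 5 still apply.

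**What to change.** 1. Reword the trigger in 7.1.1 iii) a) to: AST or ALT >2 x baseline, OR total bilirubin >1.5 x baseline and above ULN. In known Gilbert's syndrome, apply the bilirubin limb to direct bilirubin, which the chemistry panel already measures.
2. State that the third-party Medical Monitor instructs the site to draw the repeat within 48-72 h, without disclosing ALT or AST values.
3. Keep the stop bullets effective at once, so that no stop waits for the repeat.
4. Secondary: change bullet 2 to baseline >=2 x ULN, with no upper limit.

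The ULN floor removes most trivial bilirubin repeats. The protocol does not state the laboratory's ULN. If it lay near the 1.3 mg/dL entry limit, the firing point for a baseline of 0.5 would move from 0.75 to 1.3 mg/dL, and the floor would matter only for baselines below 1.3/1.5 = 0.87 mg/dL.

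The cost is amendment wording, one notification step and some extra unscheduled liver tests. No new assay is needed, and the ALT/AST values stay blinded, although a repeat request will itself tell the site that a liver value needs checking.

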- a. MRI is the preferred imaging modality. There must be no nodules with a Liver Imaging and Reporting Data System (LI-RADS) score of ≥ 2 by central radiologist evaluation.
- b. If MRI is not available or not possible to be performed, a multi-phasic CT scan may be used to assess HCC risk. There must be no nodules with a LI-RADS score ≥ 2 by central radiologist evaluation.
- c. If MRI and CT are not available or not possible to be performed for screening a potential subject, then ultrasonography of the liver may be performed:
 - 1) If no hepatic lesions or nodules (local radiologist evaluation) and AFP ≤ 20 ng/mL, the potential subject may be considered further for enrollment.
 - 2) For any findings of hepatic lesions or nodules (local radiologist evaluation) that are not clearly benign cysts and have not been shown clearly benign by prior CT or MRI, follow-up MRI must be performed and meet criteria (no nodules with LI-RADS score of ≥ 2 evaluated centrally) in order for the potential subject to be considered further for enrollment.

7. Subjects with T2D or insulin resistance are permitted as long as diabetic medications are reasonably “stable” within 3 months prior to Screening, as outlined in [Section 6.4](#).
8. Other concomitant medications/therapies used for the treatment of coexisting conditions are acceptable ([Section 6.4](#)), if on a stable regimen for at least 3 months prior to the Screening, except for non-statin lipid lowering agents, which can be used until Day 1 of Screening.
9. Statin use is acceptable based on the following criteria, as assessed by the investigator at Screening:
 - a. **Statin-naïve** is defined as no administration of statins within 3 months prior to Screening
 - b. **Statin-Experienced** is defined as currently receiving $\leq 50\%$ of the maximal approved dose of statin therapy
Requires a reasonably stable statin dose at least 3 months prior to Screening

Note: The following are the acceptable daily doses of approved statin therapies, and other lipid lowering agents. Also listed under [Section 6.4](#):

- i. Atorvastatin: ≤ 40 mg/day
- ii. Fluvastatin: ≤ 40 mg/day
- iii. Lovastatin: ≤ 40 mg/day (for both immediate and extended release)
- iv. Pitavastatin: ≤ 2 mg/day
- v. Pravastatin: ≤ 40 mg/day

vi. Simvastatin: ≤ 40 mg/day

vii. Rosuvastatin: ≤ 20 mg/day

10. The following additional laboratory parameters must be met at Screening

- a. Total bilirubin ≤ 1.3 mg/dL

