 - i. if Gilbert's Syndrome, with direct bilirubin within ULN.
- b. HbA1c $\leq 9.5\%$
- c. Platelet count $\geq 120,000/\text{mm}^3$

Subjects who meet the Baveno VI criteria with a platelet count $>110,000/\text{mm}^3$ and $<120,000/\text{mm}^3$ may be enrolled if they meet the expanded Baveno VI criteria. (Note: No more than 30% of the remaining population will be enrolled using the Baveno VI criteria.)

- d. Creatinine clearance ≥ 60 mL/min as calculated by Cockcroft-Gault equation
- e. Serum alanine amino transferase (ALT) levels $\leq 5 \times \text{ULN}$
- f. Serum aspartate amino transferase (AST) levels $\leq 5 \times \text{ULN}$
- g. Alkaline phosphatase $\leq 1.5 \times \text{ULN}$
- h. Serum albumin ≥ 3.5 g/dL
- i. International normalized ratio (INR) ≤ 1.7 .

Note: A 10% laboratory variability is allowed on platelets and bilirubin values.
Platelet variability does not apply to Baveno VI.

11. Female subjects must be either of a) non-childbearing potential, defined as women who have had a hysterectomy, bilateral oophorectomy, medically documented ovarian failure, documented postmenopausal, or a follicle stimulating hormone ≥ 40 mIU/mL, OR b) if of childbearing potential, defined as including women <55 years of age with ≤ 2 years of amenorrhea (absence of menstruation and not due to any reversible medical cause or any current medication use), then have a negative serum pregnancy test at Screening and urine pregnancy test at the Day 1 visit prior to first dose of study drug, and must be non-lactating and non-breastfeeding. Note: Females who do not meet this criterion can be included if they meet Inclusion Criterion 12.

12. Female subjects of childbearing potential and male subjects with a female partner of childbearing potential must agree to consistent and adequate birth control from Screening to EOS (Week 54):

- Recommended forms of contraception for males: condom, vasectomy, and sexual abstinence
 - i. Vasectomized partner is a highly effective birth control method provided that the partner is the sole sexual partner of the female subject of childbearing potential trial participant and that the vasectomized partner has received medical assessment of the surgical success.

- ii. Condom use is not considered as a highly effective form of contraception alone and may be used effectively with a second method of contraception.

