7. STUDY TREATMENT DISCONTINUATION AND SUBJECT DISCONTINUATION / WITHDRAWAL FROM THE STUDY

7.1. Discontinuation of Study Treatment for an Individual Subject

Study treatment discontinuation, interruption or dose reduction will be considered if subjects experience the following:

- TEAE of Grade 3 or 4 (per CTCAE V5.0) with severity and relationship noted below
- Any suspected statin-related AE, as determined by the investigator (see below)
- Laboratory result(s) indicative of drug induced liver disease (DILI), based on assessment by the Medical Monitor and by the independent DILI adjudication
- Confirmed diagnosis of HCC
- Progression from Child-Pugh A to Child-Pugh B or C status
- Liver decompensation events
- Subjects with MELD score ≥ 15 .

7.1.1. Specific Actions Taken Will Be As Follows:

- i) TEAE of Grade 3 or 4 (per CTCAE V5.0):
 - Any possibly or probably related Grade 3 TEAE, aldafermin and/or statin may be discontinued or interrupted; evaluation and determination by the PI or the unblinded Medical Monitor in the case of TEAEs possibly related to statin use.
 - Any Grade 4 or higher TEAE, aldafermin and statin will be discontinued
- ii) Any suspected statin-related AE:

Subjects will be allowed a rosuvastatin dose adjustment if the subject experiences a statin-related AE (as determined by the PI). The third-party Medical Monitor will be contacted by the study site to report a possible statin-related AE requiring intervention. Information will be collected on the AE including the specific description, history, and severity based on CTCAE grading. The study team should instruct the subject to refrain from administering the rosuvastatin/placebo therapy and to repeat safety laboratory examinations as indicated by the specific AE within 72 hours. If the subject is <2 weeks from their next visit, they should not dose the rosuvastatin/placebo therapy until the next scheduled visit. If they are >2 weeks from their next study visit, an unscheduled visit should be made to repeat laboratory examinations.

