7.2. Discontinuation of Subjects from Study Participation

Subjects will be informed that they are free to withdraw from the study at any time and for any reason. The PI may remove a subject from the study if, in the PI's opinion, it is not in the best interest of the subject to continue the study. Subjects may be discontinued due to a change in compliance with an inclusion/exclusion criterion that is clinically relevant and affects subject safety, occurrence of AEs, occurrence of pregnancy, or administration of non-permitted concomitant medication that might affect subject safety or study assessments/objectives. In addition, for any AEs noted, the PI will determine whether there is impact, or a potential for impact, on subject safety or study assessments/objectives, and will remove such subjects. Subjects will be discontinued due to clinically relevant changes in a subject's status related to Inclusion and Exclusion criteria that significantly affect subject safety or study integrity, development of pregnancy, or necessary administration of non-permitted concomitant medications that might affect subject safety or study assessments/objectives. Notification of discontinuation will be made immediately to the sponsor Medical Monitor or designee. In case of premature discontinuation of study participation, efforts will be made to perform all final EOT and EOS visits/assessments. The date the subject is withdrawn from the study and the reason for discontinuation will be recorded on the subject's Case Report Form (CRF). All withdrawn subjects will be followed until resolution of any AEs or until any unresolved AEs are judged by the PI to have stabilized.

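### The enzyme-only stop limits in Section 7.1.1 iii) b) end just below a baseline of 5 × ULN, while entry admits ALT and AST up to and including 5 × ULN

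*Protocol*

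**What the plan says.** Protocol Section 7.1.1 iii) b) lists when aldafermin and rosuvastatin will be stopped or interrupted for suspected DILI. Two bullets depend on ALT or AST alone:

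- BLM below 2 × ULN: stop when ALT or AST exceeds 5 × BLM.
- The next band: "If BLM $\geq 2 \times$ ULN but $<5 \times$ ULN, discontinue if ALT or AST increases to $>3 \times$ BLM".

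There is no enzyme-only bullet for BLM of 5 × ULN or more. The remaining bullets apply at every baseline but need something besides the enzymes: a bilirubin or INR rise alongside ALT or AST above 2 × BLM, total bilirubin above 3.0 mg/dL, or symptoms, signs or eosinophilia.

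Section 5.1, Inclusion Criterion 10, opens "The following additional laboratory parameters must be met at Screening". Items 10e and 10f then allow ALT and AST up to 5 × ULN with 5 included.

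The only definition of baseline for the liver rules is in iii) a), where the subject-specific value is "calculated using the average of the Day -56 and the Day 1 values". In iii) b) BLM is expanded only as baseline measurements.

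**The concern.** The entry criterion includes the value 5 × ULN and the stopping rule excludes it, so an eligible subject can fall outside both enzyme-only bands. The entry cap is tied to Screening while the baseline also uses Day 1, so the gap may reach a little above 5.0.

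At stake is a numeric safety limit in subjects with cirrhosis, at the highest baselines the trial admits. Two features make a written number useful there. Table 8, footnote j, blinds sites and sponsor to ALT and AST from Week 2, so an investigator may not see an isolated rise; the decision lies with those who do see the values. And the 48–72 hour repeat test in iii) a) requires a bilirubin rise as well as an enzyme rise, so an isolated enzyme rise does not trigger it.

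**Working it through.** **Inputs from the protocol.** Bands and multipliers: Section 7.1.1 iii) b). Entry cap ≤5 × ULN: Inclusion 10e/10f. Baseline = (Day -56 + Day 1)/2: iii) a), carried over to BLM in iii) b) by inference. Planned subjects: 150.

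**1. Stop limit as written, in multiples of ULN**

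| BLM | Rule | Limit as written | Limit with no upper bound |
|---|---|---|---|
| 1.99 | 5 × BLM | >9.95 | >9.95 |
| 2.0 | 3 × BLM | >6.0 | >6.0 |
| 4.9 | 3 × BLM | >14.7 | >14.7 |
| 4.99 | 3 × BLM | >14.97 | >14.97 |
| 5.0 | none | none | >15.0 |
| 5.2 | none | none | >15.6 |

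**2. Which baselines can reach the gap.** BLM ≥5 requires Day 1 ≥ 10 − (Day -56). Since Day -56 ≤5, Day 1 must be at least 5.0.

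- If the Day 1 value must also be ≤5 × ULN, the only solution is 5.0 at both visits: a single point.
- If Day 1 is not capped, BLM can go somewhat higher. As an illustration only, suppose Day 1 could exceed Day -56 by the 35% that Exclusion 7 tolerates between Day -56 and Day -42. Then BLM could reach (5 + 6.75)/2 = 5.875, and a Day -56 value of 5/1.175 ≈ 4.26 × ULN would be enough to reach 5.0.

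The protocol does not settle which reading applies. Section 8.2.3 has eligibility reassessed before dosing on Day 1. It also places the Day 1 chemistry draw, randomization and first dose in the same visit, with no instruction to wait for the result.

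**3. How many subjects.** The protocol gives no figure, so this is a simulation on assumptions, with 2,000,000 lognormal subjects per setting.

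- Baselines from Table 3 (non-cirrhotic NASH): ALT 74.3 (SD 33.9) or 81.4 (48.6); AST 50.6 (27.5) or 61.3 (34.2) U/L.
- Assumed: within-subject CV 15–30%; ALT–AST correlation 0.8 between and 0.7 within subjects; ULN as shown below.
- Entry: Day -56 ALT and AST ≤5 × ULN, and Exclusion 7 met.

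| Assumed ULN (U/L) | Probability that BLM ≥5 × ULN, Day 1 uncapped | × 150 |
|---|---|---|
| ALT 50, AST 45 | 0.00019–0.00185 | 0.03–0.28 |
| 40 | 0.00099–0.00531 | 0.15–0.80 |
| 35 | 0.00250–0.00930 | 0.38–1.40 |
| 30 | 0.00541–0.01660 | 0.81–2.49 |

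For ULN 35–50 the expected number is 0.03 to 1.4. The chance of at least one such subject is 1 − (1 − 0.00019)^150 ≈ 3% to 1 − (1 − 0.0093)^150 ≈ 75%. Adding within-subject variation on top of the Table 3 SD, instead of counting it within that SD, gives about 0.07 to 1.9. With Day 1 capped at 5 × ULN the simulated count is 0.

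**The case against.** The strongest reply is that this is a strict-versus-inclusive inequality slip with almost no consequence. Much of it stands.

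- **The narrow reading is plausible.** Eligibility is reassessed on Day 1 before randomization. If that enforces the cap, only 5.0 × ULN at both visits is affected.
- **The baseline definition is inferred.** Applying the iii) a) average to BLM in iii) b) is natural but not written. Every non-zero count depends on that inference and on Day 1 being uncapped.
- **The counts measure falling into the gap, not harm.** Harm would also need an isolated, asymptomatic rise above 3 × BLM. If 1–10% of such subjects had one (an assumption; the protocol gives no rate), 0.03 × 0.01 = 0.0003 to 1.4 × 0.10 = 0.14 subjects remain. Section 2.7 also reports that aldafermin lowered mean ALT and AST in earlier NASH cohorts.
- **Other cover exists.** Section 7.1 has DILI discontinuation considered "based on assessment by the Medical Monitor and by the independent DILI adjudication". The lead-in to iii) b) weighs "factors that include how much higher than baseline ALT and AST were relative to the ULN". Section 7.2 states: "Subjects will be discontinued due to clinically relevant changes in a subject's status related to Inclusion and Exclusion criteria that significantly affect subject safety". Clinically relevant laboratory changes count as adverse events (Section 8.4.1), and any Grade 4 treatment-emergent event stops both drugs.

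A reader might infer that high-baseline subjects have no liver stopping rule, or that no other rule supplies an enzyme number. The first is wrong, given the cover above. The second cannot be established: Section 7.1.1 i) grades by CTCAE V5.0, which is not reproduced in the protocol. Nor does the blinding mean that nobody sees the enzymes: Sections 7.1.1 ii) and 8.3.17 give a third-party Medical Monitor access to laboratory results.

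What the reply does not remove is the mismatch itself. Iii) b) fixes a mandatory enzyme-only limit at 4.99 × ULN and none at 5.0, and an eligible subject can be at 5.0.

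**Conclusion.** The point holds as a narrow boundary gap and is minor. The mismatch between the bands and the entry cap follows directly from the text. Its width does not: it is a single value if Day 1 eligibility enforces 5 × ULN. Otherwise it affects roughly 0 to 2 of 150 subjects for an assumed ULN of 35–50 U/L, somewhat more at 30 U/L, with BLM taken as the Day -56/Day 1 average and baselines borrowed from a non-cirrhotic population. These subjects lack a mandatory limit in iii) b) for an isolated, asymptomatic rise; they do not lack protection altogether. The efficacy analysis is not affected.

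**What to change.** In the next amendment, remove the upper bound from the second bullet of Section 7.1.1 iii) b), so that it reads: if BLM ≥2 × ULN, discontinue if ALT or AST increases to >3 × BLM. The limits for every BLM below 5 × ULN stay as they are, and the Day 1 question no longer matters for this rule.

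The cost is one deleted phrase and at most a rare extra interruption. Alternatives are a strict entry limit of <5 × ULN, an inclusive upper bound in the second bullet, or a separate and possibly stricter top band. The first two leave a BLM above 5 × ULN uncovered if Day 1 is not capped. A stricter top band would be a clinical choice for the sponsor.
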